# Study setting

The geographical area covered by this study is within the city of Newcastle; care to this area is provided by the Newcastle upon Tyne Hospitals NHS Foundation Trust Community services.

# Criteria for Withdrawal/Discontinuation/exit

- The duration of patient participation in the study is 8 weeks.
- Patient participation in the study will be terminated immediately in case of discomfort or intolerance to zinc or calamine or any allergen present in the dry bandages as per standard procedure.
- Each participant has the right to withdraw from the study at any time without prejudice.
   In addition, the investigator may advise that a participant be discontinued from the study at any time if the investigator considers it necessary for any reason; however withdrawal decisions remain with the participant at all times.
- The investigator may withdraw a subject at any time, for any reason.
- The reasons for withdrawal and discontinuation for any subject shall be recorded.
- Any data and information collected for the subject up until the time of withdrawal or discontinuation, may still be included in the study registry, unless the participant has asked that their data are not to be used. The site shall document all requests by participants regarding their data use.
- Where participants lose capacity to consent during their time in the study, they will be withdrawn from further follow up; however data collected until this point will be retained for use. No further data would be collected, or any other research procedures conducted in relation to the participant.

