# Compression bandage selection procedure

The choice to apply 'full compression' versus 'reduced compression' will be dictated by the aetiology of the ulcer, wound assessment etc as per standard care. However, one leg will be bandaged in 'paste' compression and one leg in 'dry' compression, through a process of randomisation, using pre-prepared sealed envelopes.

The two types of compression bandages that will be used in this study are 'standard care' and are:

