# Timeline

Each patient participant will be consented at time of recruitment. A patient information sheet will be offered. Each leg will be randomised to either  $S_1F/S_1R$ ,  $S_2F/S_2R$  or  $S_3F/S_3R$ . The Research Nurse will visit each patient participant where they receive their treatment at Week 0, Week 1, Week 4, and Week 8. All participants will have demographic data obtained and the following outcome measures (Table 1):

Weeks	0	1	4	8
Baseline measures (demographics, medical history, vascular history; nursing teams and setting)	~			
Visual analogue pain score (pre, during and after dressing change)	~	~	~	~
Visual analogue pruritus score	~	~	~	~
EQ-5D-5L	~			~
VEINES-QoL	~			~
Patient and Nurses Experience		
 
✓
 
	~	~
questionnaire				
Nurses technical questionnaire		✓	~	~
Photo(s) of both legs	~	✓	✓	✓

Table 1. Outcome measures

- a) Baseline measures (see Appendix 1)
- b) Visual analogue pain score (see Appendix 2)
- c) Visual analogue pruritus score (see Appendix 2)

- d) VEINES-QoL is a patient reported outcome measure score that focuses on lower limb health (see Appendix 2)
- e) EQ-5D-5L is a general quality of life measurement tool (see Appendix 2)
- f) Patient questionnaire for comfort at application, during wear and on removal, fluid handling (see Appendix 3).

During the recruitment process the research team will acts as a contact point and coordinator for patients requiring information and support. If concerns are raised on participants (mental) wellbeing based on the home visits or outcome of the assessments, referral of patients/families on to other professional agencies will be done as appropriate and according to the Trust guideline.

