# **APPENDIX 3. PATIENT AND NURSE'S EXPERIENCE** PATIENT AND NURSE QUESTIONNAIRE – CLINICAL EXPERIENCE

Bandage used: Right Leg S1F/S1R, S2F/S2R or S3F/ S3R (circle what applies)	S1F = UrgoK2 S1R = UrgoK2 Lite S2F = Coban2 S2R = Coban2 Lite S3F = AndoFlex TLC Calamine S3R = AndoFlex TLC Lite Zinc
FOR THE PATIENT TO COMPLETE	
Please rate the following as your overall experience of circle):	of wearing this bandage (please
Has this bandage helped with your pain?	Yes No N/a
Has this bandage improved your comfort?	Yes No N/a
Has this bandage improved your ability to wear normal footwear and clothes?	Yes No N/a
Has this bandage stayed in place?	Yes No N/a
Has this bandage improved your skin condition?	Yes No N/a
Has this bandage improved your skin irritation?	Yes No N/a
Please add any further comment of your personal experience	
FOR THE NURSE TO COMPLETE	
Prior to last bandage application, was the leg washed with Hydromol mixed in warm water?	Yes No N/a
Prior to last bandage application, was the leg debrided using a debridement cloth or tenatome?	Yes No N/a
Looking at the leg, has this bandage helped improve the leg's skin condition?	Yes No N/a
Looking at the leg, has this bandage reduced the leg's skin irritation?	Yes No N/a
Looking at the leg, has this bandage helped with wound healing?	Yes No N/a

Looking at the leg, has this bandage helped with wound

malodour?

Yes

No N/a

	S1F = UrgoK2
	S1R = UrgoK2 Lite
Bandage used: Left Leg	
	S2F = Coban2
S1F/S1R, S2F/S2R or S3F/ S3R (circle what applies)	S2R = Coban2 Lite
	S3F = AndoFlex TLC Calamine
	S3R = AndoFlex TLC Lite Zinc

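### A reaction to one leg's bandage ends the whole patient's participation, and adjacent bullets disagree on whether the investigator may withdraw a participant

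*Protocol*

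**What the plan says.** **Exit after a reaction.** Under Criteria for Withdrawal/Discontinuation/exit, the Protocol says "Patient participation in the study will be terminated immediately in case of discomfort or intolerance to zinc or calamine or any allergen". The sentence goes on to place those allergens in the dry bandages and to call this standard procedure. The same section lets data gathered before exit be used unless the participant objects, and adds: "The reasons for withdrawal and discontinuation for any subject shall be recorded".

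**Allocation and rating.** Under Compression bandage selection procedure, "one leg will be bandaged in 'paste' compression and one leg in 'dry' compression", by randomisation. Both questionnaires in Appendix 3 have separate right-leg and left-leg sections. Table 1 schedules them at Weeks 1, 4 and 8. The visit plan is: "The Research Nurse will visit each patient participant where they receive their treatment at Week 0, Week 1, Week 4, and Week 8".

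**Comfort as an outcome.** The outcome list under Timeline includes "Patient questionnaire for comfort at application, during wear and on removal, fluid handling", and Appendix 3 asks of each leg's bandage: "Has this bandage improved your comfort".

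**Who decides withdrawal.** One bullet lets the investigator advise discontinuation, then adds "however withdrawal decisions remain with the participant at all times". The next bullet reads: "The investigator may withdraw a subject at any time, for any reason".

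**The concern.** **Level of the stop.** The study asks for whom and in what circumstances each bandage type suits. The Project summary gives patients who cannot tolerate compression, and for whom other systems were not considered, as the reason for the project. A patient who reacts to one product while wearing the other type on the opposite leg is directly informative on that question. The rule takes this patient out of all later visits. The Protocol has no provision for stopping one bandage while follow-up continues. What is observed at later visits therefore leans towards patients who tolerated both products.

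**Authority to withdraw.** If the investigator advises withdrawal and the participant declines, one bullet keeps the participant in the study and the next allows removal. No order of precedence is given, so the same disagreement could end either way. The mandatory stop after a reaction is also hard to square with leaving every withdrawal decision to the participant.

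**Working it through.** The Protocol gives no figure for reactions, dropout or power, so there is no stated result to reproduce. The check is a reading of the text plus a count from Table 1.

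**1. Unit of stop against unit of allocation.**
- Exit criteria: the patient's participation ends.
- Compression bandage selection procedure: one leg paste, one leg dry. Zinc and calamine are named only in the paste products, so intolerance to them arises from the paste leg's bandage.
- Appendix 3: each leg's bandage is rated separately.

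The exit bullet does not mention a single leg. The consequence follows from putting these places together: intolerance to the paste bandage also ends assessment of the dry leg, and the reverse. The reference to standard procedure does not confine the stop to the affected leg.

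**2. Timing.** Recruiting and Screening says bandages are changed 2 to 3 times per week. The first experience rating is at Week 1, and Table 1 has no exit assessment. A reaction in the first days can therefore leave only a recorded reason.

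**3. Leg-level questionnaire sections lost per patient.** Loss = questionnaires × 2 legs × remaining visits. The maximum counts both questionnaires, with a nurse taking part at every visit. The minimum counts only the patient's part of one questionnaire, because nurse participation is voluntary.

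| Exit | Visits left | Minimum | Maximum | Of which other leg |
|---|---|---|---|---|
| Before Week 1 | 3 | 1×2×3 = 6 | 2×2×3 = 12 | 3 to 6 |
| After Week 1 | 2 | 1×2×2 = 4 | 2×2×2 = 8 | 2 to 4 |
| After Week 4 | 1 | 1×2×1 = 2 | 2×2×1 = 4 | 1 to 2 |

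Photographs of both legs at the remaining visits are lost as well. EQ-5D-5L and VEINES-QoL at Week 8 are also missed, but they describe the whole person or both legs, so they are not counted as bandage-specific loss.

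**4. Illustration of scale (assumed rates only).** Let each leg's bandage trigger the stop with probability p. If the legs are independent, the share of patients leaving is 1 − (1 − p)². With dependence it lies between p (full overlap) and 2p (no overlap).

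| Assumed p | Patients leaving, independent | Range | Of 40, remaining (independent) |
|---|---|---|---|
| 5% | 1 − 0.95² = 9.75% | 5–10% | about 36 |
| 10% | 1 − 0.90² = 19% | 10–20% | about 32 |
| 20% | 1 − 0.80² = 36% | 20–40% | about 26 |

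Nothing in the Protocol favours any of these rows.

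**5. The two withdrawal bullets.** They agree when the participant accepts the advice. They give opposite answers when the participant declines.

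**The case against.** **The pair is broken anyway.** Once one bandage stops, the patient's randomised paste/dry contrast is over, and ending participation after a reaction is a cautious safety rule. The first part stands: later ratings are descriptive and must be kept apart from the randomised comparison. The second part does not require study exit, because stopping the bandage at once gives the same protection.

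**The important information survives.** Earlier data may be kept and the reason is recorded, which suits a realist evaluation with descriptive and thematic analysis. This stands and is why the loss is modest. It does not help the patient who leaves before any rating.

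**Continuing only the other leg would do harm.** Patients intolerant of paste would then add later dry ratings but no paste-leg ratings, turning a symmetric loss into a differential one. This stands, and the remedy has to follow both legs.

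**Stronger readings to avoid.**
- A reader might infer that an outcome, comfort, doubles as an exit criterion. That holds only if discomfort means any discomfort. The sentence can equally be read as discomfort from the named substances.
- A reader might infer an imbalance in numbers between paste and dry. Both legs leave together, so the rule produces none.

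**Investigators need power to act on safety.** Agreed. The defect is that the two bullets conflict, not that such a power exists.

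**Conclusion.** Both parts hold and should be corrected.

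The patient-level stop discards later leg-level data that could still be collected at visits already planned, and it does so for patients central to the research question. Under either reading of discomfort, the stop is at patient level. The loss per patient ranges from 2 to 12 leg-level sections, depending on when exit occurs and whether nurses take part. How many patients are affected is unknown, and the Protocol does not support a claim of large or quantified bias. With earlier data kept, reasons recorded and a descriptive analysis, the overall effect is modest.

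The conflict over withdrawal authority is explicit in the text and needs no assumption. Resolving it takes a single rule; the Protocol gives no basis for a detailed closed list of investigator grounds.

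**What to change.** **1. Reword the reaction bullet**, for example:

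> In case of intolerance or allergic reaction to a bandage, or discomfort the patient does not wish to continue with, that bandage is stopped immediately and the leg receives standard care. The existing experience questionnaire for the stopped bandage is completed at the stop or the next contact, and the leg, bandage and reason are recorded. With the participant's agreement, scheduled visits and assessments of both legs continue to Week 8. Ratings after the stop are labelled with the bandage then worn and reported separately from the randomised paste/dry comparison.

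**2. Replace the conflicting statements on investigator withdrawal with one rule**, for example:

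> The investigator may stop a study bandage at any time, and may end participation for safety or loss of capacity; otherwise the investigator may advise withdrawal and the participant decides.

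The participant's right to leave without prejudice, and the existing provision on loss of capacity, stay as they are.

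**Cost.** A protocol amendment, probably with ethics review because a safety-exit criterion changes; a check that the patient information sheet agrees; and a few extra fields on the record. No visits are added: the already scheduled ones are kept for these patients (three, two or one, depending on when the bandage stops). The Safety section says that two brands on one patient are not unusual in standard care, so a changed bandage on one leg should be workable.

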# Participant inclusion/exclusion criteria

Patient Inclusion

- Age  $\geq$  18 years of age
- Patient living in Newcastle upon Tyne, with a Newcastle GP.
- Patients with **existing** bilateral leg ulceration or legs that require compression bandages to prevent ulcer (re)-occurrence.
- Patients with **new** bilateral leg ulceration or legs that require compression bandages to prevent ulcer (re)-occurrence.

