# Patient Exclusion

- Patient younger < 18 years of age
- Patients in nursing homes
- Patients with leg ulcerations that do not necessitate compression bandages.
- Patients with leg ulcerations that require a specific type of compression bandages (i.e. lymphoedema)

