# **Recruiting and Screening**

Patients will be existing patients on the Newcastle upon Tyne Hospitals NHS Foundation Trust District Nursing's workload. Potential patients participants will be identified using Systm1, the electronic documentation system used by District Nurses in Newcastle. A list of potential participants will be drawn by the administrative team within District Nurses.

During the course of standard care, District Nurses will ask permission for the Research Nurse to contact them via telephone, letter or email. With agreeing, the District Nurse will enter the following text in the patient electronic documentation: "Mr/Mrs/Ms [Patient name] has agreed for the Research Nurse to contact him/her regarding the ROSE study". Upon contact, the Research Nurse will give potential patient participants the PIS and seek informed consent.

Thus Nurse participants will be involved in the recruitment process, and it is hoped that this will enhance their willingness to be recruited to the study alongside their patients.

Nurse Participants will be contacted by the Research Nurse who is a NuTH employee, through the existing nursing management structure.

In accordance with Good Clinical Practice, participation in this study is voluntary and any decision not to participate will not have any impact on how the subject's clinical treatment is performed. Patients will have a minimum of 24h to decide whether to participate or until the following visit by the District Nurses team (compression bandages are changed 2-3 times per week).

Following recruitment, a participant will be considered enrolled once he/she signs and dates the informed consent form. Once enrolled, the participant will be assigned a unique subject number, which will not contain information that could identify him/her (such as name or date of birth). The unique participant number will be used to label study data throughout the study.

All District Nurses in the organisation will be sent the Patient Information Sheet by their managers so that they will be well informed about the study aim and objectives. The research nurse might observe the application of compression bandaging. Patients receive care by a group of District Nurses, it is not unusual for patients to see 10-12 different District Nurses during the course of their treatment. Nurse participation is voluntary.

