# a) Paste bandages:

 $S_3F$  – full compression (F): AndoFlex TLC Calamine (Milliken, USA) - a two-layer compression bandage. The first layer is a soft foam layer impregnated with Calamine. The second layer is a cohesive short-stretch bandage.  $S_3R$  – reduced compression (R): AndoFlex TLC Lite Zinc (Milliken, USA), a two-layer

compression bandage. The first layer is a soft foam layer impregnated with Zinc. The second layer is a cohesive short-stretch bandage.

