# Reporting of safety events and device complaints

This study involves the use of licensed Class I CE Mark post-market compression bandages currently used in standard practice and is not expected to pose additional medical risks to the patients beyond those of a routine clinical treatment.

Anticipated risks can be associated to misuse (e.g. poor compression bandage application techniques) and allergy to the bandages components.

In the very unlikely event that a Serious Adverse Event (SAE) has to be reported, a form has been devised. For the purpose of this study, a SAE has been defined as: an adverse event that led to death; led to a serious deterioration in the health of the subject, users, or other persons as defined by; either resulted in a life-threatening illness or injury, a permanent impairment of a body structure or a body function, or in-patient or prolonged hospitalisation, or medical or surgical intervention to prevent life-threatening illness or injury or permanent impairment to body structure or a body function; or led to foetal distress, foetal death or a congenital abnormality or birth defect.

Planned hospitalisation for a pre-existing condition, or a procedure required by the protocol without serious deterioration in health, is not considered a Serious Adverse Event.

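### Intolerance to a bandage component is an exit rule and an anticipated risk, but nothing asks about a known one before the sealed envelope sets paste or dry

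*Protocol*

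**What the plan says.** **Exit.** Under Criteria for Withdrawal/Discontinuation/exit, participation stops immediately for discomfort or for "intolerance to zinc or calamine or any allergen present in the dry bandages as per standard procedure". The rule is written for the patient, not for one leg. Data gathered up to that point may be kept unless the patient objects.

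**Risk.** Reporting of safety events and device complaints gives two sources of anticipated risk: misuse, and "allergy to the bandages components".

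**Entry.** The inclusion criteria cover age, residence and GP, and bilateral ulceration (existing or new) or "legs that require compression bandages to prevent ulcer (re)-occurrence". The nearest exclusion reads "Patients with leg ulcerations that require a specific type of compression bandages (i.e. lymphoedema". Neither list mentions allergy or sensitivity.

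**Screening and enrolment.** Recruiting and Screening runs from an administrative list drawn from the electronic record, to permission for contact, to the information sheet and consent. Then "a participant will be considered enrolled once he/she signs and dates the informed consent form".

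**Allocation.** In Compression bandage selection procedure, the choice of full or reduced compression is "dictated by the aetiology of the ulcer, wound assessment etc as per standard care". Paste or dry is not left to that assessment: "one leg will be bandaged in 'paste' compression and one leg in 'dry' compression", set by randomisation with sealed envelopes. The full-compression paste product is described as follows: "The first layer is a soft foam layer impregnated with Calamine". The reduced-compression paste product is impregnated with zinc.

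**Baseline.** Appendix 1 records comorbidities (eczema, psoriasis and other dermatitis among them), the wound dressing and the skin care product. It has no item on allergy, sensitivity or a past reaction to a bandage.

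**The concern.** The protocol treats component intolerance as serious enough to end participation at once, but applies it only at exit. The same fact, if already known, is not a stated bar to entry.

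The gap matters more here than in routine care because the study takes over the decision at which a known allergy would normally be acted on. A nurse choosing freely can avoid a product. Here the envelope chooses between paste and dry, and the nurse's remaining discretion concerns compression level. Changing the level does not avoid an impregnated paste layer, since both paste products have one.

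Two things are at stake. The first is safety: a patient could be exposed to something already known to cause a reaction. The second is avoidable loss: an exit removes the whole patient, so later observation of both legs stops even if only one bandage was at fault. If the allergy comes to light after consent, the patient is already enrolled and is recorded as a withdrawal rather than screened out. A prior reaction is also relevant to the study's own question of for whom each bandage type is suitable, yet it would reach the record only by chance.

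**Working it through.** The protocol states no figure on this point, so there is none to reproduce. The check takes each place where a pre-allocation question could sit and asks two things: does it name allergy or intolerance, and does it act before the envelope is opened?

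| Place in the protocol | Names allergy or intolerance? | Acts before allocation? |
|---|---|---|
| Inclusion criteria | No | Yes |
| Patient Exclusion | No; the closest item concerns ulcers that need a particular bandage type, glossed as lymphoedema | Yes |
| Recruiting and Screening | No | Yes |
| Compression bandage selection procedure | No; assessment sets the level only | At allocation |
| Timeline, Week 0 medical history | Not named | Order relative to the envelope not stated |
| Appendix 1 | No; the comorbidity list is open-ended, so an allergy could be noted | Order not stated; not tied to eligibility |
| Safety | No; a general assurance of usual care | Not specific |
| Withdrawal criteria | Yes | No stated pre-allocation role |
| Reporting of safety events | Yes, as an anticipated risk | No |

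No row has a yes in both columns. The two sections that name the hazard do not screen for it, and the sections that screen do not name it.

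**From eligibility to allocation.** Take a patient with a known reaction to calamine who needs full compression on both legs.
1. The patient meets the inclusion criteria and no exclusion names the reaction.
2. The patient signs consent and is enrolled.
3. Assessment sets full compression.
4. Under the selection procedure one leg is assigned paste, and the full-compression paste product contains calamine.

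The same steps hold for a zinc reaction with reduced compression. For a dry-bandage allergen they hold if the dry system assigned contains it.

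**How many patients?** The protocol gives no prevalence of known component allergy. As an illustration only, assume a prevalence p among those enrolled without a screen, and 40 independent patients. The expected number is 40p and the chance of at least one is 1 − (1 − p)^40.

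| Assumed p | Expected number | Chance of at least one |
|---|---|---|
| 0 | 0 | 0 |
| 1% | 0.4 | 33% |
| 2% | 0.8 | 55% |
| 5% | 2.0 | 87% |
| 10% | 4.0 | 99% |

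These rows count patients who have a known allergy, not patients who are exposed. Exposure also needs the component to be in the allocated bandage and the allergy to go undisclosed or unheeded. The protocol gives no basis for either probability.

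**The case against.** The strongest reply is that being allocated a bandage is not the same as having it applied. Participants come from an existing caseload with an electronic clinical record, registered nurses do the bandaging, the products are already standard in the Trust, and the Safety section promises the care patients would otherwise receive. The investigator may withdraw anyone at any time. Read literally, the exit rule could also end participation at Week 0, before any bandage goes on. This stands as a reason to expect that some, perhaps all, known cases would be caught. It does not supply a stated check, and it leaves a patient caught after consent recorded as a withdrawal. The phrase about standard procedure in the exit rule describes stopping, not screening.

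A second reply is that the exclusion for ulcers needing a specific bandage type could be read to cover allergy. Its wording concerns what the ulcer requires, and its only gloss is lymphoedema, so the reading is strained.

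A third is that the exit rule also covers discomfort, and that reactions first discovered during the study will still cause exits. This is correct. Screening removes only cases already known.

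A fourth stands in full: the study was prompted by patients who report that they cannot tolerate compression, so a loosely worded intolerance exclusion could remove the people it most needs. The fix has to be worded around that.

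**Conclusion.** The gap is real and lies in eligibility, which is protocol content and not something to leave to an analysis plan. As written, a patient with a known allergy to a bandage component is eligible and may be allocated that component. The textual absence is certain. The consequence is unquantified: the number affected is unknown and may be zero, and routine care may catch some cases. The amendment is worth making because it is cheap and concerns a risk that the protocol itself names.

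A reader might infer more than the documents support, in three ways.
- *That patients with known allergies will be exposed.* This would require routine nursing checks to fail, and nothing shows that they would.
- *That all 40 patients are certain to wear paste.* The selection procedure says so, but the Timeline section says each leg is randomised among three systems, which does not by itself guarantee paste.
- *That the loss can be expressed as a share of leg-visits.* Only the Appendix 3 bandage questionnaires and the photographs are plainly recorded by leg. The pain and itch scales in Appendix 2 name no side. VEINES-QoL and EQ-5D-5L are completed once per patient, at Weeks 0 and 8. No single per-leg denominator fits, and the analysis is descriptive and thematic with no powered comparison stated.

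The benefit of acting is therefore patient safety and fewer foreseeable whole-patient exits, not a measurable gain in precision.

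**What to change.** 1. Add to Patient Exclusion: known (documented or patient-reported) allergy or sensitivity reaction to zinc, calamine or a component of the study bandages.
2. In Recruiting and Screening, require this to be checked in the clinical record and with the patient before the envelope is opened. Doing it at the screening contact, ahead of consent, would make a positive answer a screening failure rather than a withdrawal.
3. Log those screened out, with the component concerned, since this bears on which patients each bandage suits.
4. State that general discomfort with compression, or past difficulty tolerating it, is not an exclusion.

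The cost is one eligibility line, one screening question and a short log in an amendment. The components of the study bandages must be listed, because the protocol names the paste impregnants but not the allergens in the dry systems. A few candidates will be screened out, some of whom might have tolerated the product they would have been allocated. Exits for discomfort or for newly discovered reactions will continue.
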